6.3.2 Dose Adjustment Guidelines for Selinexor-Related Toxicities

Table 4: Criteria for Dose Adjustments for Selinexor-related Toxicities

Toxicity and Intensity	Dose Modification		
	Part 1: 50 mg/m ² twice weekly	Part 2, Schedule 1: 35 mg/m ² twice weekly – Ovarian only	Part 2, Schedule 2: 50 mg/m ² once weekly – Ovarian only
Fatigue (common)			
Grade 1	Ensure adequate caloric intake and assess volume status. Adjust other medications. Rule out other causes of fatigue such as electrolyte imbalance, hyperglycemia.	Ensure adequate caloric intake and assess volume status. Adjust other medications. Rule out other causes of fatigue such as electrolyte imbalance, hyperglycemia.	Ensure adequate caloric intake and assess volume status. Adjust other medications. Rule out other causes of fatigue such as electrolyte imbalance, hyperglycemia.
Grade 2	
 1. As in grade 1 2. Consider patient diary to evaluate fluid and food intake. 3. Add medroxyprogesterone acetate (MPA) (ovarian and cervical only) or 4 mg dexamethasone (or equivalent) on day after selinexor dosing. 4. In case of dehydration add IV fluids on the dosing day. 5. If fatigue does not resolve to grade 1 or baseline, reduce one dose level of selinexor 6. For additional support see NCCN guidelines^a. 	
 1. As in grade 1 2. Consider patient diary to evaluate fluid and food intake. 3. Add MPA or 4 mg dexamethasone (or equivalent) on day after selinexor dosing. 4. In case of dehydration add IV fluids on the dosing day. 5. If fatigue does not resolve to grade 1 or baseline, reduce one dose level of selinexor 6. For additional support see NCCN guidelines^a. 	
 1. As in grade 1 2. Consider patient diary to evaluate fluid and food intake. 3. Add MPA or 4 mg dexamethasone (or equivalent) 3 days post dosing of selinexor. 4. In case of dehydration add IV fluids on the dosing day. 5. If fatigue does not resolve to grade 1 or baseline, reduce one dose level of selinexor 6. For additional support see NCCN guidelines^a.
Grade 3 mm ³	As in grade 2; if symptoms not resolved within 7 days, interrupt selinexor dosing until symptoms return to grade 1 or baseline and restart treatment with one dose reduction of selinexor	As in grade 2; if symptoms not resolved within 7 days, interrupt selinexor dosing until symptoms return to grade 1 or baseline and restart treatment with one dose reduction of selinexor	As in grade 2; if symptoms not resolved within 7 days, interrupt selinexor dosing until symptoms return to grade 1 or baseline and restart treatment with one dose reduction of selinexor

Toxicity and Intensity	Dose Modification		
	Part 1: 50 mg/m ² twice weekly	Part 2, Schedule 1: 35 mg/m ² twice weekly – Ovarian only	Part 2, Schedule 2: 50 mg/m ² once weekly – Ovarian only
Anorexia/Weight Loss (common)			
Grade 1	Ensure adequate caloric intake and assess volume status. Adjust other medications. Rule out other causes of anorexia/weight loss such as electrolyte imbalance, hyperglycemia	Ensure adequate caloric intake and assess volume status. Adjust other medications. Rule out other causes of anorexia/weight loss such as electrolyte imbalance, hyperglycemia	Ensure adequate caloric intake and assess volume status. Adjust other medications. Rule out other causes of anorexia/weight loss such as electrolyte imbalance, hyperglycemia
Grade 2	
 As grade 1 Consider patient diary to evaluate fluid and food intake. Add MPA (ovarian and cervical only) or 4 mg dexamethasone (or equivalent) on day after selinexor dosing. In case of dehydration add IV fluids on the dosing day. If anorexia dose not resolve to Grade 1 or baseline, reduce one dose level of selinexor For additional supportive care see NCCN guidelines^b 	
 As grade 1 Consider patient diary to evaluate fluid and food intake. Add MPA or 4 mg dexamethasone (or equivalent) on day after selinexor dosing. In case of dehydration add IV fluids on the dosing day. If anorexia dose not resolve to Grade 1 or baseline, reduce one dose level of selinexor For additional supportive care see NCCN guidelines^b 	
 As grade 1 Consider patient diary to evaluate fluid and food intake. Add MPA or 4 mg dexamethasone (or equivalent) 3 days post dosing of selinexor. In case of dehydration add IV fluids on the dosing day. If anorexia dose not resolve to Grade 1 or baseline, reduce one dose level of selinexor For additional supportive care see NCCN guidelines^b
Grade ≥ 3 (Grade 4 for anorexia only)	
 As in grade 2 Add MPA (ovarian and cervical only) or megestrol acetate If symptoms not resolved within 7 days, interrupt selinexor dosing until resolved to grade 1 or baseline and restart treatment with one dose reduction of selinexor 	
 As in grade 2 Add MPA or megestrol acetate If symptoms not resolved within 7 days, interrupt selinexor dosing until resolved to grade 1 or baseline and restart treatment with one dose reduction of selinexor 	
 As in grade 2 Add MPA or megestrol acetate If symptoms not resolved within 7 days, interrupt selinexor dosing until resolved to grade 1 or baseline and restart treatment with one dose reduction of selinexor
Nausea/Emesis (common)			
Grade 1	5-HT3 antagonists, D2 antagonists as needed. Consider adding 4 mg dexamethasone (or equivalent) on day after selinexor dosing.	5-HT3 antagonists, D2 antagonists as needed. Consider adding 4 mg dexamethasone (or equivalent) on day after selinexor dosing.	5-HT3 antagonists, D2 antagonists as needed. Consider adding 4 mg dexamethasone (or equivalent) on day after selinexor dosing.

Grade 2	Implement one or more combinations of anti-nausea medications. Next dose add neurokinin-1 receptor (NK1R) antagonist (e.g., aprepitant) prophylactic. If nausea does not resolve to Grade ≤ 1 or baseline, reduce one dose level of selinexor. Consider NK1R antagonist as prophylaxis next cycle. For additional options see NCCN guidelines for antiemesis. ^c	Implement one or more combinations of anti-nausea medications. Next dose add NK1R antagonist (e.g., aprepitant) prophylactic. If nausea does not resolve to Grade ≤ 1 or baseline, reduce one dose level of selinexor. Consider NK1R antagonist as prophylaxis next cycle. For additional options see NCCN guidelines for antiemesis. ^c	Implement one or more combinations of anti-nausea medications. Next dose add NK1R antagonist (e.g., aprepitant) prophylactic. If nausea does not resolve to Grade ≤ 1 or baseline, reduce one dose level of selinexor. Consider NK1R antagonist as prophylaxis next cycle. For additional options see NCCN guidelines for antiemesis. ^c
Grade ≥ 3 (Grade 4 for emesis only)	As in grade 2; if symptoms persist hold dose until nausea and vomiting resolve to grade 1 or baseline. Restart dose of selinexor, one dose below. Start NK1R antagonist as prophylaxis next cycle.	As in grade 2; if symptoms persist hold dose until nausea and vomiting resolve to grade 1 or baseline. Restart dose of selinexor, one dose below. Start NK1R antagonist as prophylaxis next cycle.	As in grade 2; if symptoms persist hold dose until nausea and vomiting resolved to grade 1 or baseline. Restart dose of selinexor, one dose below. Start NK1R antagonist as prophylaxis next cycle.
Hematologic			
Neutropenia			
Grade ≤ 3	
 Maintain dose level The use of growth factors during selinexor treatment is permitted and in patients with poor marrow function, encouraged. If ANC drops to < 1000/mm³, growth factors are encouraged to reduce dose interruptions. 	
 Maintain dose level The use of growth factors during selinexor treatment is permitted and in patients with poor marrow function, encouraged. If ANC drops to < 1000/mm³, growth factors are encouraged to reduce dose interruptions. 	
 Maintain dose level The use of growth factors during selinexor treatment is permitted and in patients with poor marrow function, encouraged. If ANC drops to < 1000/mm³, growth factors are encouraged to reduce dose interruptions.
Grade 4 (ANC < 500/mm ³)	
 Delay study treatment until ANC returns to > 800/mm³, then: If increased to > 800/mm³ by ≤ 7 days after suspending selinexor, maintain dose level If increased to > 800/mm³ by > 7 days after suspending selinexor, then reduce one dose level. The use of growth factors during selinexor treatment is encouraged. 	
 Delay study treatment until ANC returns to > 800/mm³, then: If increased to > 800/mm³ by ≤ 7 days after suspending selinexor, maintain dose level If increased to > 800/mm³ by > 7 days after suspending selinexor, then reduce one dose level. The use of growth factors during selinexor treatment is encouraged. 	
 Delay study treatment until ANC returns to > 800/mm³, then: If increased to > 800/mm³ by ≤ 7 days after suspending selinexor, maintain dose level If increased to > 800/mm³ by > 7 days after suspending selinexor, then reduce one dose level The use of growth factors during selinexor treatment is encouraged.

Febrile neutropenia, or fever of unknown origin without clinically or microbiologically documented infection (ANC < 1.0 x 10 ⁹ /L, fever ≥ 38.5°C)	1. Delay study treatment until patient has stabilized, then reduce selinexor one dose level. 2. Selinexor may be re-initiated at the reduced dose when patient's condition has stabilized following initiation of antibiotic therapy. 3. Selinexor dose may be re-escalated after ≥ 1 cycle at the reduced dose provided ANC is adequate.	1. Delay study treatment until patient has stabilized, then reduce selinexor one dose level. 2. Selinexor may be re-initiated at the reduced dose when patient's condition has stabilized following initiation of antibiotic therapy. 3. Selinexor dose may be re-escalated after ≥ 1 cycle at the reduced dose provided ANC is adequate.	1. Delay study treatment until patient has stabilized, then reduce selinexor one dose level. 2. Selinexor may be re-initiated at the reduced dose when patient's condition has stabilized following initiation of antibiotic therapy. 3. Selinexor dose may be re-escalated after ≥ 1 cycle at the reduced dose provided ANC is adequate.
Thrombocytopenia (Platelets)			
Grade ≤ 2	Maintain dose level	Maintain dose level	Maintain dose level
Grade ≥ 3 without bleeding	
First occurrence: Delay selinexor treatment until resolved to ≤ grade 1 or baseline (max 4 weeks), and restart at 50 mg/m² once a week. Thrombocyte growth factors (e.g., romiplostim, eltrombopag, oprelvekin) are recommended.
 
Second occurrence: Delay selinexor treatment until resolved to ≤ grade 1 or baseline (max 4 weeks), and restart at 35 mg/m² once a week. Start treatment with thrombocyte growth factors.
 
Third occurrence: stop treatment
	
First occurrence: Delay selinexor treatment until resolved to ≤ grade 1 or baseline (max 4 weeks), and restart at 50 mg/m² once a week. Thrombocyte growth factors (e.g., romiplostim, eltrombopag, oprelvekin) are recommended.
 
Second occurrence: Delay selinexor treatment until resolved to ≤ grade 1 or baseline (max 4 weeks), and restart at 35 mg/m² once a week. Start treatment with thrombocyte growth factors.
 
Third occurrence: stop treatment
	
First occurrence: Delay selinexor treatment until resolved to ≤ grade 1 or baseline (max 4 weeks), and restart at 35 mg/m² once a week. Thrombocyte growth factors (e.g., romiplostim, eltrombopag, oprelvekin) are recommended.
 
Second occurrence: Delay selinexor treatment until resolved to ≤ grade 1 or baseline (max 4 weeks), and restart at 35 mg/m² once a week. Start treatment with thrombocyte growth factors.
 
Third occurrence: stop treatment


≥ Grade 3 Thrombocytopenia associated with purpura or bleeding
	
 1. Delay selinexor treatment until resolved to ≤ grade 1 or baseline (max 4 weeks), and restart at 35 mg/m² once a week. 2. Transfuse platelets per institutional guidelines. If medically indicated, discontinue any anti-platelet agents. Implement platelet growth factors and/or transfusions. Platelet growth factors may require 2-4 weeks to take effect, and should be maintained until platelets are consistently > 100,000/mm³. 	
 1. Delay selinexor treatment until resolved to ≤ grade 1 or baseline (max 4 weeks), and restart at 35 mg/m² once a week. Transfuse platelets per institutional guidelines. If medically indicated, discontinue any anti-platelet agents. Implement platelet growth factors and/or transfusions. Platelet growth factors may require 2-4 weeks to take effect, and should be maintained until platelets are consistently > 100,000/mm³. 2. When purpura or bruising resolves, restart selinexor at level -1. 	
 1. Delay selinexor treatment until resolved to ≤ grade 1 or baseline (max 4 weeks), and restart at 35 mg/m² once a week. Transfuse platelets per institutional guidelines. If medically indicated, discontinue any anti-platelet agents. Implement platelet growth factors and/or transfusions. Platelet growth factors may require 2-4 weeks to take effect, and should be maintained until platelets are consistently > 100,000/mm³. 2. When purpura or bruising resolves, restart selinexor at level -1.

Platelet Stimulators
	
The use of platelet stimulators is encouraged in patients with a history of thrombocytopenia or compromised marrow function, or in patients in whom selinexor is having demonstrable disease control. IL-11 (oprelvekin), eltrombopag, or romiplostin should be considered.
	
The use of platelet stimulators is encouraged in patients with a history of thrombocytopenia or compromised marrow function, or in patients in whom selinexor is having demonstrable disease control. IL-11 (oprelvekin), eltrombopag, or romiplostin should be considered.
	
The use of platelet stimulators is encouraged in patients with a history of thrombocytopenia or compromised marrow function, or in patients in whom selinexor is having demonstrable disease control. IL-11 (oprelvekin), eltrombopag, or romiplostin should be considered.

Hyponatremia (common)
			

Grade 1 (Lower Limit of Normal to 130 nM)
	
Maintain dose level, assure adequate fluid, electrolyte and caloric intake, adjust other medications, consider salt supplementation, rule out other causes.
	
Maintain dose level, assure adequate fluid, electrolyte and caloric intake, adjust other medications, consider salt supplementation, rule out other causes.
	
Maintain dose level, assure adequate fluid, electrolyte and caloric intake, adjust other medications, consider salt supplementation, rule out other causes.

Grade ≥ 3 (120-130 nM)
	
Discontinue selinexor until resolved to grade ≤ 1, then reduce dose by 1 level. Check renal function, serum, and urinary electrolytes, and rule out other causes.
	
Discontinue selinexor until resolved to grade ≤ 1, then reduce dose by 1 level. Check renal function, serum, and urinary electrolytes, and rule out other causes.
	
Discontinue selinexor until resolved to grade ≤ 1, then reduce dose by 1 level. Check renal function, serum, and urinary electrolytes, and rule out other causes.

AST or ALT (rare)
			

Grade 1 (> ULN - 2.5 x ULN)
	
Maintain dose level
	
Maintain dose level
	
Maintain dose level

Grade 2 (> 2.5 - 5.0 x ULN)	Delay selinexor until resolved to grade \leq 1 or baseline, then maintain dose level. Consider addition of S-adenosylmethionine (SAM) 400 mg qd-bid.	Delay selinexor until resolved to grade \leq 1 or baseline, then maintain dose level. Consider addition of S-adenosylmethionine (SAM) 400 mg qd-bid.	Delay selinexor until resolved to grade \leq 1 or baseline, then maintain dose level. Consider addition of S-adenosylmethionine (SAM) 400 mg qd-bid.
Grade 3 (> 5.0 - 20.0 x ULN)	
 1. Delay selinexor until resolved to \leq grade 2 or baseline, then reduce by 1 dose level (Table 2 & Table 3) 2. Consider addition of S-adenosylmethionine (SAM) 400 mg qd-qid. 3. If no further AST or ALT elevations occur during one cycle (4 weeks) at the reduced dose level, then dose may be continued at the reduced dose. 4. Discontinuation of selinexor is required if concurrent elevations of direct bilirubin > 2.0 X upper limit of normal (ULN) and ALT or AST > 3.0 X ULN are observed. 5. In order to characterize hepatic toxicity more precisely, fractionation of bilirubin and alkaline phosphatases will be required for elevated values > 2.0 X ULN and \geq CTCAE grade 2, respectively. 	
 1. Delay selinexor until resolved to \leq grade 2 or baseline, then reduce by 1 dose level (Table 2 & Table 3) 2. Consider addition of S-adenosylmethionine (SAM) 400 mg qd-qid. 3. If no further AST or ALT elevations occur during one cycle (4 weeks) at the reduced dose level, then dose may be continued at the reduced dose. 4. Discontinuation of selinexor is required if concurrent elevations of direct bilirubin > 2.0 X upper limit of normal (ULN) and ALT or AST > 3.0 X ULN are observed. 5. In order to characterize hepatic toxicity more precisely, fractionation of bilirubin and alkaline phosphatases will be required for elevated values > 2.0 X ULN and \geq CTCAE grade 2, respectively. 	
 1. Delay selinexor until resolved to \leq grade 2 or baseline, then reduce by 1 dose level (Table 2 & Table 3) 2. Consider addition of S-adenosylmethionine (SAM) 400 mg qd-qid. 3. If no further AST or ALT elevations occur during one cycle (4 weeks) at the reduced dose level, then dose may be continued at the reduced dose. 4. Discontinuation of selinexor is required if concurrent elevations of direct bilirubin > 2.0 X upper limit of normal (ULN) and ALT or AST > 3.0 X ULN are observed. In order to characterize hepatic toxicity more precisely, fractionation of bilirubin and alkaline phosphatases will be required for elevated values > 2.0 X ULN and \geq CTCAE grade 2, respectively.
Grade 4 (> 20.0 x ULN)	Delay selinexor until resolved to \leq grade 2, then reduce by 2 dose levels.	Delay selinexor until resolved to \leq grade 2, then reduce by 2 dose levels.	N/A
Diarrhea (common)			
Grade 1 (despite maximal anti-diarrheal medication)	At the first sign of abdominal cramping, loose stools, or onset of diarrhea, it is recommended that the patient be treated according to institutional standard of care. Maintain dose level of selinexor.	At the first sign of abdominal cramping, loose stools, or onset of diarrhea, it is recommended that the patient be treated according to institutional standard of care. Maintain dose level of selinexor.	At the first sign of abdominal cramping, loose stools, or onset of diarrhea, it is recommended that the patient be treated according to institutional standard of care. Maintain dose level of selinexor.

Grade 2 (despite maximal anti-diarrheal medication)	First occurrence: reduce selinexor to once weekly until resolved to ≤ grade 1, then re-start twice weekly at the current dose level. Second occurrence: reduce selinexor dose by one dose level and dose once weekly until resolved to ≤ grade 1, then re-start twice weekly at reduced dose level	First occurrence: reduce to selinexor to once weekly until resolved to ≤ grade 1, then re-start twice weekly at the current dose level. Second occurrence: reduce selinexor dose by one dose level and dose once weekly until resolved to ≤ grade 1, then re-start twice weekly at reduced dose level	First occurrence: reduce selinexor to 35 mg/m ² until resolved to ≤ grade 1 or baseline, then re-start at the Dose level 0. Second occurrence: reduce one dose level
Grade 3/4 (despite maximal anti-diarrheal medication)	Delay selinexor until resolved to ≤ grade 2 or baseline, then follow guidelines above.	Delay selinexor until resolved to ≤ grade 2 or baseline, then follow guidelines above.	Delay selinexor until resolved to ≤ grade 2 or baseline then reduce one dose level.
Other selinexor-related adverse events			
Grade 1 or 2	Maintain dose level and initiate standard supportive care.	Maintain dose level and initiate standard supportive care.	Maintain dose level and initiate standard supportive care.
Grade 3	Delay dose until resolved to ≤ grade 1 or baseline, then reduce by one dose level.	Delay dose until resolved to ≤ grade 1 or baseline, then reduce by one dose level.	Delay dose until resolved to ≤ grade 1 or baseline, then reduce to Dose level -1.
Grade 4	Discontinue selinexor and rule out other causes. If other causes of grade 4 adverse event are uncovered, selinexor may be re-started at a reduced dose level	Discontinue selinexor and rule out other causes. If other causes of grade 4 adverse event are uncovered, selinexor may reduce in 2 dose level	Discontinue selinexor and rule out other causes. If other causes of grade 4 adverse event are uncovered, selinexor may be re-started at a reduced dose level.

All dose modifications should be based on the worst preceding toxicity.

Isolated values of ≥ grade 3 alkaline phosphatase values will NOT require dose interruption. Determination of liver vs bone etiology should be made, and evaluation of gamma-glutamyl transferase (GGT), 5'-nucleotidase (5'NT), or other liver enzymes should be performed.

≥ Grade 3 anemia judged to be a hemolytic process secondary to study drug will require interruption of study treatment until resolved to ≤ grade 1. Selinexor may then be re-instituted at 1 level below original dose (Table 2 and Table 3).

≥ Grade 3 lymphopenia considered clinically significant will require dose interruption until resolved to ≤ grade 2, then reduce by 1 dose level.

Patients are allowed dose reductions to a minimum dose of 35 mg/m² once weekly for Part 1 and Part 2 (Schedules 1 and 2) as described in Table 2 and Table 3, respectively.

If a patient requires a dose interruption of > 28 days, then the patient must be discontinued from the study. Patients who discontinue the study for a study-related adverse event or abnormal laboratory value must be followed at least once a week for 28 days and subsequently at 28-day intervals until resolution or stabilization of the event, whichever comes first.

Common Terminology Criteria for Adverse Events (CTCAE Version 4.03) or otherwise specified values.

^aNational Comprehensive Cancer Network[®]. NCCN Clinical Practice Guidelines in Oncology (NCCN Guidelines[®]): Fatigue. Available at http://www.nccn.org/professionals/physician_gls/pdf/fatigue.pdf.

^bNational Comprehensive Cancer Network[®]. NCCN Clinical Practice Guidelines in Oncology (NCCN Guidelines[®]): Palliative Care, version 2.2015. Fort Washington, NY. May 2015. Available at: <http://www.nccn.org/content/nationalcontent/resourcecenter/freeeducationmaterials/generalcancer/pdf/facts.pdf>. Attached as Appendix 11.

^cNational Comprehensive Cancer Network[®]. NCCN Clinical Practice Guidelines in Oncology (NCCN Guidelines[®]): Antiemesis, version 1.2015. Fort Washington, NY. April 2015. Available at: http://www.nccn.org/professionals/physician_gls/PDF/antiemesis.pdf. Attached as Appendix 10.

For patients whose dose has been reduced due to neutropenia, anorexia or fatigue, dose re-escalation is permitted if the institution of supportive care measures has reduced these toxicities to Grade ≤ 1 or to baseline for at least 2 weeks. Dose re-escalation is only permitted for these adverse events when supportive measures have been successful.

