Endometrial cancer generally carries a favorable prognosis, mainly because the majority of women present with bleeding early on in the disease course. As a result, the disease is caught early and for most women the disease is curable by surgery; 5-year survival rates of 80% to 90% are generally reported.^{56,57} However, for women with advanced stage disease or high-risk histologies, the prognosis is poor, with 5-year survival rates of 57% for regional disease (stage III) and 19% for distant spread (stage IV).¹

The overall rate of recurrence for endometrial cancer is about 15%, with more than half occurring within 2 years of primary treatment. Recurrence rates for patients with early stage disease range from 2% to 15%, whereas it is up to 50% in women with advanced stage disease or in patients with aggressive histologies (grade 3 or non-endometrioid).^{58,59,60}

In the setting of recurrent disease, certain clinico-pathologic factors are associated with a good prognosis, including a longer disease-free interval, low-grade and endometrioid histology, and isolated recurrence at the vaginal cuff. The disease in women with non-endometrioid histologies (uterine serous carcinoma and clear cell) behaves more aggressively and carries a significantly worse prognosis in regard to response to chemotherapy and overall survival.

Although non-endometrioid histologies, such as uterine serous cancer and clear cell, constitute < 10% of all cases of endometrial cancer, they account for a disproportionately high number of cancer-related deaths and cases of recurrence.⁶¹⁻⁶⁶ The poor prognosis associated with serous tumors, in particular, may be due to their advanced disease at the time of diagnosis.⁶⁴

In addition to isolated vaginal recurrences, patients may present with disease isolated to the pelvis, which is considered a loco-regional recurrence. For these patients, treatment is similar to the management of metastatic disease.

Survival rates for women whose disease recurs outside of the pelvis are dramatically lower than those for women with a local, vaginal relapse. In fact, they are comparable to those of women with distant disease.⁶⁷

For women with metastatic disease, the predominant modality of treatment is systemic therapy with either endocrine therapy or chemotherapy. However, the prognosis for these patients is poor. Cytotoxic chemotherapy has activity in endometrial cancer with response rates ranging from 7 to 25%. See [Table 8 \(Appendix 3\)](#)⁶⁸⁻⁸³.

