4.2.2 Exclusion criteria

Patients who meet any of the following exclusion criteria will not be eligible for the study:

Patients with any of the following will not be eligible for participation:

1. Disease-Specific Exclusions:
 - Evidence of complete or partial bowel obstruction.
 - Need of Total Parenteral Nutrition.
2. Patients who are pregnant or breast feeding.
3. Radiation (except planned or on-going palliative radiation to bone outside of the region of measurable disease) ≤ 3 weeks prior to Cycle 1 Day 1.
4. Chemotherapy, endocrine therapy, immunotherapy or any other systemic anti-cancer therapy (including investigational anti-cancer therapy) ≤ 3 weeks prior to Cycle 1 Day 1.
5. Diagnosis or recurrence of invasive cancer other than the present cancer within

-
- 3 years (except basal or squamous cell carcinoma of the skin that has been definitively treated).
6. Unstable cardiovascular function:
 - Symptomatic ischemia, or
 - Uncontrolled clinically significant conduction abnormalities (e.g. ventricular tachycardia on anti-arrhythmics are excluded and 1st degree AV block or asymptomatic LAFB/ RBBB will not be excluded), or
 - Congestive heart failure (CHF) of NYHA Class \geq 3, or myocardial infarction (MI) within 3 months of Cycle 1 Day 1.
 7. Uncontrolled active infection requiring parenteral antibiotics, antivirals, or antifungals within one week prior to the first dose. Active infection with concurrent treatment is acceptable only if the patient is clinically stable.
 8. Significantly diseased or obstructed gastrointestinal tract or uncontrolled vomiting or diarrhea.
 9. Concurrent therapy with approved or investigational anti-cancer therapeutics.
 10. Medical, psychological, or social conditions that may interfere with the patient's participation in the study or evaluation of the study results.
 11. Known brain metastases unless adequately treated (surgery or radiotherapy) with no evidence of progression and neurologically stable off anticonvulsants and glucocorticoids.
 12. All non-epithelial cancers of the ovary, fallopian tube, peritoneum, endometrium or cervix as well as neuro-endocrine tumors are excluded.

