6.4.2 Restricted and Prohibited Medications

6.4.2.1 Concurrent Therapies

Concurrent therapy with any other approved or investigative anticancer therapeutic is not allowed. Other investigational agents should not be used during the study. Use of any immunosuppressive agents during the study must be confirmed by the Medical Monitor. Note that the use of denosumab is not allowed.

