6.5.2 Supportive Care Recommendations for Selinexor-Related Adverse Events

Supportive measures for optimal medical care should be provided during participation in this clinical trial. Based on clinical observations in over 560 adult patients treated with selinexor with evaluable safety data as of 01 February 2015, the main side effects are primarily related to anorexia with poor caloric and fluid intake, fatigue, and nausea. Thrombocytopenia also occurs, although it is rarely associated with bleeding.

Besides the required 5-HT3 (Section 6.5.1), supportive care including anti-nausea / anti-emetic therapy, acid suppression (proton pump inhibitors and/or H2-blockers) and other treatments may be administered as described below:

1. Glucocorticoids: dexamethasone (4-12 mg) or equivalent glucocorticoid (e.g., prednisone 10-20 mg) on days of, and 1 day after, selinexor dosing may improve appetite, reduce nausea or vomiting, and minimize fatigue. A maximum of 40 mg dexamethasone or equivalent may be given per week.
2. Appetite stimulants: megestrol acetate at a dose of 80-400 mg daily.
3. Centrally acting agents: per National Comprehensive Cancer Network® (NCCN) Clinical Practice Guidelines® for antiemesis⁹⁸ and anorexia/cachexia (palliative care)⁹⁹ see [Appendix 10](#) (antiemesis) and [Appendix 11](#) (anorexia), respectively.
4. NK1R antagonist: aprepitant or equivalent should be considered and will be covered for selected patients who have severe nausea and vomiting.

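### Endometrial cohort: one progestin (MPA) is withheld but another (megestrol acetate) is not, and the readable SAP does not separate a progestin effect from selinexor disease control

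*Protocol*

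**What the plan says.** **Supportive care.** Protocol 6.3.2, Table 4, Part 1 column, limits MPA to ovarian and cervical patients in three places:
- Fatigue Grade 2: "Add medroxyprogesterone acetate (MPA) (ovarian and cervical only) or 4 mg dexamethasone (or equivalent) on day after selinexor dosing".
- Anorexia/weight loss Grade 2: "Add MPA (ovarian and cervical only) or 4 mg dexamethasone (or equivalent) on day after selinexor dosing".
- Anorexia/weight loss Grade 3 or higher, step 2: "Add MPA (ovarian and cervical only) or megestrol acetate".

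Part 1 has three cohorts, so the limit removes endometrial patients only. The Part 2 columns, which cover ovarian patients alone, do not carry it. Megestrol acetate has no cohort limit in Table 4. Section 6.5.2 also lists it among treatments that may be given to any patient: "Appetite stimulants: megestrol acetate at a dose of 80-400 mg daily".

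**Anticancer therapy.** The endometrial part of Section 1.1.1 says of metastatic disease that "the predominant modality of treatment is systemic therapy with either endocrine therapy or chemotherapy". Exclusion 4 in Section 4.2.2 covers "Chemotherapy, endocrine therapy, immunotherapy or any other systemic anti-cancer therapy" in the 3 weeks before Cycle 1 Day 1; the synopsis version of that exclusion does not name endocrine therapy. On study, Section 6.4.2.1 states: "Concurrent therapy with any other approved or investigative anticancer therapeutic is not allowed".

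**Analysis.** SAP 4.3.1 counts CR, PR or SD lasting at least 77 days as disease control, cohort by cohort. SAP 3.6 plans no covariate adjustment. SAP 3.10 has no censoring at the start of a progestin. SAP 4.5.8 tabulates and lists concomitant medications without linking them to efficacy.

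**The concern.** The protocol withholds one progestin from the cohort in which, on its own account, endocrine therapy is a main treatment, and leaves another open to the same patients. No passage says how supportive-care megestrol in Cohort B stands against the ban on concurrent anticancer therapy, or whether its use is a protocol violation under SAP 2.2. Use that follows Table 4 could be judged compliant and stay in the per-protocol set, or be judged prohibited and removed.

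Cohort B has no control arm, and the primary endpoint rewards stability as well as shrinkage. A tumour held stable by a progestin would look the same as one held stable by selinexor, and any such bias runs toward declaring activity. The trigger is foreseeable: Section 6.5.2 says "the main side effects are primarily related to anorexia with poor caloric and fluid intake, fatigue, and nausea".

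**Working it through.** **1. Reconstruct the decision rule.** The sample size sections are redacted, so the rule has to be inferred.
- Null and alternative DCR: 0.25 and 0.50 (Protocol 8.1).
- One-sided alpha: 0.10 (SAP 3.2).
- Stage 1 of 8 patients, with 3 or more disease control achievers named as the early trigger (Protocol 8.5).
- About 21 evaluable patients per cohort (Protocol 3.2).
- Power: not readable; 80% assumed.

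An exact search for Simon's optimal design on these inputs returns: continue at 3 or more of 8, succeed at 8 or more of 21. This matches the stated 8, 3 and 21. Its exact alpha is 0.098 and its power 0.811. At 85% or 90% power the optimal total would be 24 or 27, which does not match.

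**2. Model the progestin effect.** Let f be the share of Cohort B given megestrol, and d the share of those not controlled by selinexor whose disease megestrol controls. With a true selinexor DCR of 0.25:

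apparent DCR = 0.25 + 0.75 × f × d

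**3. Chance of a positive Cohort B conclusion.** With p the apparent DCR, this is the sum over x = 3 to 8 of P(X1 = x) × P(X2 ≥ 8 − x), where X1 ~ Bin(8, p) and X2 ~ Bin(13, p).

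| f | d | Apparent DCR | P(positive) |
|---|---|---|---|
| 0 | – | 0.25 | 0.098 |
| 5% | 10% | 0.25375 | 0.105 |
| 10% | 10% | 0.2575 | 0.112 |
| 20% | 10% | 0.265 | 0.128 |
| 30% | 20% | 0.295 | 0.201 |
| 40% | 30% | 0.34 | 0.338 |

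The documents give neither f nor d. The table shows how sensitive the rule is; it does not estimate the bias.

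**4. What remains for Cohort B at Grade 3 or higher anorexia/weight loss.** Step 1 of that cell repeats the Grade 2 measures, so dexamethasone, IV fluids and dose reduction still apply. In step 2, with MPA withheld, megestrol is the only agent left.

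**The case against.** The strongest reply is that the documents never call megestrol a progestin, give no reason for the MPA limit, and list megestrol only as an appetite stimulant. Section 6.5.2 is permissive, and a supportive-care permission can stand beside a ban on anticancer drugs. This stands to the extent that the passages are unreconciled; they are not in flat contradiction. The shared drug class is general pharmacology and is stated here as such.

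A second reply is that exposure may be small. The Table 4 instruction applies at Grade 3 or higher, and Protocol 1.1.2.2.1 describes the frequent events, anorexia among them, as low-grade. This also stands, and is why the table starts at 5% use, where the effect is slight.

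Third, medications are tabulated by cohort, so exposure will be visible, and SAP 4.3.3 is redacted and cannot be checked. But a tabulation does not show whether the exposed patients are the ones counted as successes.

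Three stronger readings might be inferred and are not supported:
- *Megestrol is an endometrial patient's only option.* Other measures carry over from Grade 2.
- *Comparison between cohorts is distorted.* None is planned; SAP 3.7 and 3.8 draw conclusions within each cohort separately.
- *The reported Stage 1 result of 5/8 is undermined.* The documents do not show who received megestrol. Even if two successes were removed, 3/8 would still reach the figure of 3 in Protocol 8.5. Table 4 was also revised between versions, so the wording in force for those patients is unknown.

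**Conclusion.** The concern holds as an unreconciled inconsistency with a gap in the analysis. MPA is withheld from Cohort B, megestrol acetate is not, and no readable SAP rule separates a progestin effect from selinexor disease control. The direction of any bias is toward activity.

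Its size cannot be derived from the documents. Under the reconstructed rule (80% power assumed) and a true DCR of 25%, the chance of a positive conclusion goes from 0.098 to between about 0.105 and 0.34 over the assumed range of 5 to 40% use and 10 to 30% effect. The documents do not show that any Cohort B result was affected. The case for acting is that the check is cheap and would settle the question.

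**What to change.** 1. **Protocol.** Reconcile Table 4 (fatigue and anorexia/weight-loss rows), Section 6.5.2, exclusion 4 in the body and the synopsis, and Section 6.4.2.1 for Cohort B, so that one rule covers progestins and their protocol-violation status. Which rule is for the sponsor to decide. With 3 patients on treatment in July 2016 (Protocol 1.4), rewording cannot alter accrued data, so step 2 matters more.
2. **SAP 4.3.1.** Leave the primary analysis unchanged and add a Cohort B sensitivity analysis labelled a worst-case (lower) bound. Patients who started megestrol acetate or MPA before the assessment that qualifies them for disease control count as not having it; report the number exposed. The label matters because this also fails patients whom selinexor did control.
3. **ORR.** Reclassify only responders whose progestin started before the first documented response. The 77-day point has no meaning for ORR.
4. **Reporting.** If the Cohort B conclusion differs between the two analyses, report it as not robust to progestin use.

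The cost is protocol wording, an extra result for Cohort B and a possibly less favourable second figure. No new data are needed: SAP 4.5.8 already codes concomitant medications with the WHO Drug Dictionary. Protocol 8.1 requires the SAP to be final before database lock, so the rule should be added before then. If no one was exposed, the added row will show it.
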